**Figure 3: Overview of the family linkage, NDD including ASD**

### 9.2.3.2 Congenital malformations

For the purpose of the evaluation of CM, Figure 4 and Figure 5 illustrate the registry linkage of the study participants, the paternal exposure period (3 months prior to LMP2 date), follow-up period for the offspring (from 12th or 22nd week of gestation, respectively, for Norway and Denmark and from birthdate of offspring for Sweden, to maximum 12 years of age for Denmark and Sweden and 10 years of age for Norway), and the look back periods for confounders for each linked family member (mother: minimum of 12 months prior to index date, father: minimum of 12 months prior to LMP2 date).

**Figure 4: Overview of the family linkage, CM for Norway and Denmark**

**Figure 5: Overview of the family linkage, CM for Sweden**

### 9.3 Variables

In order to meet the study objectives, the following parameters will be obtained from the selected data sources and analysed:

- Demographic characteristics for descriptive cohort
- Exposure of interest (section 9.3.1)

- Outcome parameters of interest (section 9.3.2)
- Potential confounding variables (section 9.3.3)

### 9.3.1 Exposure definition and measures

Within the AEDs, the primary exposure of interest is the dispensation of valproate. Brand names and generics of all forms of valproate salts will be considered (sodium valproate, valproic acid, valproate semisodium and valpromide) and summarized under the term “valproate”. Valproate will be identified using Anatomical Therapeutic Chemical (ATC) code N03AG01.

*Drug exposure of the offspring is based on the use of AEDs by the father during a risk window prior to conception. Since the spermatogenic cycle is approximately 2.5 months, the risk window considered here is three months prior to conception. Further details are presented in section 9.3.1.3*

As reported in section 9.7.3.2, in the primary analysis, paternal exposure to valproate (monotherapy) will be compared to paternal exposure to lamotrigine or levetiracetam (composite monotherapy). These drugs are generally associated with lower risk of teratogenicity for the offspring of women, however it is unknown whether the effect is the same in men. Lamotrigine and levetiracetam will be identified using ATC codes N03AX09 and N03AX14, respectively. Since polytherapy is indicated for medically refractory epilepsy (14), in order to avoid the risk of disease severity bias associated to polytherapy, evaluation of AED exposure according to monotherapy is preferred for comparative analyses. In this section, definitions of monotherapy and polytherapy are only discussed for AEDs. Co-medications (other than AEDs) are defined in section 9.3.3 (Potential confounding variables). Monotherapy is defined as the exposure to a single AED, whilst polytherapy is defined as any combination of AEDs (including valproate among the exposed and excluding valproate among the unexposed), simultaneously or in sequence, within the 3-months risk window. For example, switching to or switching from an AED other than valproate, lamotrigine or levetiracetam, will be considered as polytherapy, and the offspring of these fathers will be excluded from the comparative analyses. This is because a washout period is not possible in clinical practice since subjects may not be unexposed for seizure control. Including people who were exposed to more drugs of the same class, in the period of interest, could lead to uncertainty in defining which drug is associated with the outcome.

Paternal exposure to other AEDs except valproate during the 3-months risk window and also maternal and offspring exposure (section 9.3.3) to AEDs will be elucidated.

Other AEDs will be identified using ATC codes (full list defined in Annex 3. Additional Information) and include:

- N03AA - Barbiturates and derivatives
- N03AB - Hydantoin derivatives
- N03AC - Oxazolidine derivatives
- N03AD - Succinimide derivatives
- N03AE - Benzodiazepine derivatives
- N03AF - Carboxamide derivatives
- N03AG (excluding N03AG01) - Fatty acid derivatives

- N03AX (excluding N03AX09 and N03AX14) - Other antiepileptics

Different AED exposure periods are applied for the father, mother and offspring, and also for NDD (including ASD) and CM for Norway and Denmark, as shown in Figure 6 and Figure 7, respectively. For the CM analysis for Sweden, the exposure periods correspond to those specified for NDD (Figure 6). *The paternal exposure to AEDs is the exposure of interest in this study, whereas maternal and offspring exposure to AEDs are potential risk factors.* Methodologies related to the maternal and offspring exposure will be further discussed in Section 9.3.3.

### 9.3.1.1 Neurodevelopmental disorders, including autism

[figure not shown]
Two of the exposure periods are considered fixed and one not fixed.

Fixed exposure periods:

- 3-months pre-conception for father (due to spermatogenic cycle)
- 3-months pre-conception for mother (section 9.3.3)

Not fixed exposure periods:

- pregnancy duration for mother (section 9.3.3)

**Figure 6: Treatment exposure windows, NDD including ASD; CM for Sweden only**

 In order to account for potential dispensations that can have led to an intake during the 3 months look-back period under investigation, all dispensations that are recorded in the 6 months before conception that gave rise to an AED intake during the 3 months prior to conception will be considered. Because information on the exact number of days supplied is not available, patients' drug use periods will be calculated using the defined daily doses (DDD) metric as defined by the World Health Organization. For each prescription the total number of DDDs will be translated into the number of days in which the patient was treated, counting 1 DDD per day and distributing all available DDDs to the days of follow-up and allowing for the use of accumulated DDDs over time.

### 9.3.1.2 Congenital malformations

All the exposure periods are considered fixed, except one :

- 3-months pre-conception for father (due to spermatogenic cycle)
- 3-months pre-conception for mother (section 9.3.3)
- 12 or 22 weeks prior to index date for mother, respectively in Norway and Denmark (section 9.3.3)

Not fixed

- pregnancy duration for mother, in Sweden (section 9.3.3)

[figure not shown]

Figure 7: Treatment exposure windows, CM for Norway and Denmark

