## 9. RESEARCH METHODS

### 9.1 Study Design

[figure not shown]
The study will be carried out using a retrospective non-interventional longitudinal population-based cohort design conducted using secondary data derived from multiple registry databases recording longitudinal medical data in Sweden, Norway, and Denmark. The aim is to study the risk of NDD including ASD, as well as CM in offspring following paternal exposure to valproate.

For the evaluation of NDD, including ASD, the population for analysis will be comprised of live births for whom medical record linkage to mother and father is available within such registries. For the evaluation of CM, the population for analysis will be comprised of live births, stillbirths and spontaneous abortions during gestation (2nd and 3rd trimester) for whom medical record linkage to mother and father is available within such registries, for Norway and Denmark. For Sweden the corresponding population for analysis will be comprised of live births only. The primary outcome of interest is NDD, including ASD in offspring up to 12 years of age based on ICD-10 diagnostic codes, as recorded in the National Patient Registries. The secondary outcome of interest is a composite of CM diagnosed in offspring up to 12 years of age, stillbirths and spontaneous abortions-based on ICD-10 diagnostic codes, as recorded in the National Patient Registries and Medical Birth Registries. The primary exposure of interest is paternal use of valproate during the spermatogenic risk window prior to conception of the offspring (defined by the first day of the last menstrual period date plus two weeks [LMP2] of the mother within the linked family unit). Exposure information will be derived from prescription data, as recorded in the National Prescription Registries for each country (from 2005 in Sweden, 2008 in Norway and 1995 in Denmark) to 31 December 2018 for Denmark and 31 December 2019 for Sweden and Norway. Country-specific cohorts of eligible linked family units will be identified. These cohorts (in terms of aggregated results) will be combined into an all-Nordic cohort (Sweden, Norway, Denmark for the primary outcome and Norway, Denmark for the secondary outcome) where feasible to further increase validity and statistical power. An overview of the study design for the primary and secondary outcomes are provided in Figure 1 and Figure 2.

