- The empirically defined clusters will be used in the analyses of the study objectives. In the comparative analyses the exposure will be expressed as a dichotomous variable: exposure to valproate in monotherapy vs exposure to lamotrigine/levetiracetam in

---

monotherapy. The classification in cluster identified with the longitudinal K-means algorithm will be used to stratify the comparative analysis in cluster homogeneous for duration and intensity of exposure.

The K-means algorithm will be applied to maternal exposure within the 3-months period prior to LMP2 and during the reported period of gestation. However, since mothers exposed to AEDs will be excluded from the comparative analyses, these data will only be provided for descriptive purposes.

Active ingredient: valproic acid - ATC: N03AG01 - WHO DDD: 1.5 g

[figure not shown]

Figure 8: Calculation of paternal exposure in each 14-day interval during the 3-months risk window prior to conception

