#### 9.3.2.2 Congenital malformations

With the objective of investigating the risk of CM in offspring paternally exposed to valproate, all CM will be included in the comparative analysis, with the caveat that minor CM are usually under reported, therefore estimates could be under-estimated (17). However, a sensitivity analysis will be performed to address this concern (see section 9.7.5, *Broader definition of CM for secondary outcome*), for Norway and Denmark only.

The **index date (start of follow-up)** will be defined as the start of the 2nd trimester or 3rd trimester (12th or 22nd week of gestation), respectively for Norway and Denmark, and from offspring birth date for Sweden from which pregnancies will be followed up for the outcome of interest.

The **exit date/end of follow-up** will be defined as the end of the study period (31 December 2018 for Denmark and 31 December 2019 for Sweden and Norway), death, emigration (where available), reaching the age of 12 years for Denmark and the age of 10 years for Norway) or date of first diagnosis of the outcome at study, which-ever is the soonest.

The analysis of the secondary outcome of CM will be defined according to the presence of at least one of the following criteria:

- an ICD-10 code of CM among live births
- an ICD-10 code of CM in diagnosis/reason for spontaneous abortion/stillbirth (Norway and Denmark only)

The analysis will focus on all CMs, with further substratification by body system organ class. The ICD-10 codes for all CMs are presented in codelist Table 11.

---

 Period between LMP2 (date of conception) and date of birth is immortal - child must survive to be eligible and diagnosis of ASD cannot occur *in utero*

 CM will be classified according to the EUROCAT categories Guide 14 (section 3.3 in EUROCAT Subgroups of congenital anomalies (18)).

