**Maternal exposure to AEDs,** especially during pregnancy, is known to be a strong risk factor for NDD, including ASD, and CM in offspring (2). Offspring maternally exposed to AEDs (including valproate), *in utero* or three months before conception, will be described and then excluded from the comparative, sensitivity and exploratory objective analyses. Person-time exposed will be classified to take into account intensity of drug exposure during the 3-months pre-conception and pregnancy risk window (see Figure 6 and Figure 7) using the longitudinal K-means clustering (R package kml) algorithm (15) and applied to the relevant analysis. This method allows for a more precise description of exposure of mothers to drugs. More details on the application of the methodology are reported in section 9.3.1.3.

**Maternal, paternal and offspring exposure to drugs other than AEDs** (including other psychoactive treatments received) during the exposure periods described in section 9.3.1, will be considered using a polypharmacy index.

The plausibility of polypharmacy as a confounding variable or risk factor is based on evidence that polypharmacy is associated with harms including adverse drug effects, drug-to-drug interaction, hospitalization and mortality. Furthermore, there is evidence that psychoactive drugs of other therapeutic class that may often be prescribed in combination with AEDs may be a risk factor for the NDD (such as antidepressants – (6)).

There is currently no consensual definition of polypharmacy. In this study a continuous variable will be defined reflecting medication count as the basis for the exclusive definition of polypharmacy and to describe the medication burden based on the cumulative number of prescribed medications from other therapeutic class (i.e. other than AEDs) to which a relevant individual is exposed within an interval of interest. For the father, this interval would be the 3-months period prior to conception. For the mother the interval would be based on available data on medications prescribed in the three months prior to conception and during gestation period.

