### **9.3.3.2 Congenital malformations - additional considerations**

**Maternal exposure to teratogenic activity/foetal toxicity.** Offspring maternally exposed (three months prior to conception or during pregnancy) to drugs with known teratogenic (32) activity/foetal toxicity (see Annex 3. Additional Information) are at risk of developing the outcomes of interest for reasons other than valproate, i.e. due to intake of other drugs associated with the CM. These offspring will be excluded from the comparative, sensitivity and exploratory objective analyses.

**Paternal exposure to teratogenic activity.** Paternal exposure to prescription medications, has not been associated with birth defects (3). Nevertheless, offspring from fathers exposed (three months prior to conception) to drugs with known teratogenic (32) activity (based on literature regarding maternal exposure) (see Annex 3. Additional Information) will be excluded from the comparative, sensitivity and exploratory objective analyses.

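### In the CM analyses for Norway and Denmark, the maternal exposure window stops at the index date but the maternal exclusion rules do not; read literally, they select on pregnancy length

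*Protocol*

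**What the plan says.** Section 9.3.1.2 lists the maternal exposure periods for CM. Three months before conception applies everywhere. For pregnancy itself, the period is fixed at "12 or 22 weeks prior to index date for mother, respectively in Norway and Denmark"; for Sweden it is "pregnancy duration for mother, in Sweden", which is not fixed. Each maternal entry refers to section 9.3.3.

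Section 9.3.2.2 sets the CM index date at gestational week 12 in Norway, week 22 in Denmark and birth in Sweden. In Norway and Denmark the pregnancy window therefore ends where follow-up begins.

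The exclusions are worded differently:

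- **AEDs, section 9.3.3 (text after Table 4).** Offspring exposed through the mother in utero or in the three months before conception "will be described and then excluded from the comparative, sensitivity and exploratory objective analyses". The same paragraph also refers to Figures 6 and 7 for the risk window.
- **AEDs, sections 9.7.3 and 9.7.4.** The in utero wording is repeated for the comparative and exploratory analyses, with no end point.
- **Teratogens, section 9.3.3.2.** "Offspring maternally exposed (three months prior to conception or during pregnancy) to drugs" on the teratogen list are excluded from the comparative, sensitivity and exploratory analyses.

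Section 9.3.1.3 adds a third description, applying the clustering of maternal exposure "during the reported period of gestation", although only for descriptive purposes.

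**The concern.** The protocol fixes one maternal window and then states an eligibility rule that does not use it. Nowhere does it say which one defines the exclusion.

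If the exclusion wording is taken at face value, entry to the CM cohort depends on what happens after the index date. The population is live births plus second- and third-trimester losses, so how long a pregnancy lasts is tied to which kind of record it becomes. A long pregnancy has more weeks in which a dispensing can remove it, and a loss soon after the index date has almost none. Losses are then over-represented among those kept.

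Three features make this worth settling:

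- Section 9.3.3 drops the polypharmacy score for CM because offspring of teratogen-exposed parents are already excluded. The filter stands in for that adjustment, so its window has to be defined.
- The teratogen list (Table 56) is broad and includes commonly dispensed drugs such as omeprazole, ibuprofen, acetylsalicylic acid and doxycycline. Exclusions need not be rare.
- Sensitivity analysis 4 (section 9.7.5) counts every spontaneous abortion or stillbirth without a coded reason as a case. Keeping losses preferentially then acts directly on the number of cases.

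**Working it through.** The plan states no figure to reproduce. The check compares the windows and then illustrates the mechanism.

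**Inputs.** Index weeks 12 and 22 (section 9.3.2.2). Conception, LMP2, is "defined by the first day of the last menstrual period date plus two weeks" (section 9.1). A term of 40 weeks from LMP is an assumption; section 9.2.1 gives nine months on average for live births.

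**Step 1: time from conception to index.** Norway 12 − 2 = 10 weeks; Denmark 22 − 2 = 20 weeks. A term pregnancy has 40 − 2 = 38 weeks.

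**Step 2: time after the index date that only the literal rule uses.** For a term birth this is 40 − 12 = 28 weeks in Norway (28/38 = 74% of post-conception time) and 40 − 22 = 18 weeks in Denmark (18/38 = 47%). For a loss at the index week it is zero. Under section 9.3.1.2 it is zero for every pregnancy.

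**Step 3: illustration under the literal rule.** Let q be the chance of exclusion on a dispensing between conception and term. The protocol gives no value, so 1%, 10% and 30% are assumptions. With a constant hazard h = −ln(1 − q)/38, a pregnancy ending at week L is excluded with probability 1 − exp(−h(L − 2)).

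| Pregnancy ends at | q = 1% | q = 10% | q = 30% |
|---|---|---|---|
| Week 12 (Norway only) | 0.26% | 2.7% | 9.0% |
| Week 22 | 0.53% | 5.4% | 17.1% |
| Week 28 | 0.69% | 7.0% | 21.7% |
| Week 40 | 1% | 10% | 30% |

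The retention of a week-22 loss relative to a term birth is:

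- q = 1%: (1 − 0.0053)/(1 − 0.01) = 1.005
- q = 10%: (1 − 0.0539)/(1 − 0.10) = 1.05
- q = 30%: (1 − 0.1712)/(1 − 0.30) = 1.18

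**Step 4: the same pregnancies with a stop at the index date.** Within a country the chance no longer depends on length. At q = 10% it is 2.7% for every Norwegian pregnancy and 5.4% for every Danish one. A difference between the two pooled countries remains, because the post-conception window is 10 weeks in one and 20 in the other.

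**The case against.** The strongest reply is that, for AEDs, the text can be read consistently. Section 9.3.1.2 points to section 9.3.3, and section 9.3.3 points back to Figures 6 and 7, the latter being the Norway and Denmark window for CM. On that reading maternal AED exposure stops at the index date and nothing after it is used. This has force, but the exclusion sentences in 9.3.3, 9.7.3 and 9.7.4 do not say so. It also does not help with teratogens: section 9.3.1 introduces the windows as AED exposure periods, and section 9.3.3.2 gives only the uncapped wording.

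A second reply is that different windows follow from registers that begin at week 12 in Norway and week 22 in Denmark, and that assessing exposure up to cohort entry is defensible. That stands, and it supports ending the exclusion at the index date. Sections 9.7.6 and 9.9.1 do acknowledge the different index dates, but for the type and severity of CM captured, not for maternal exclusions.

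A third reply is that the same filter applies to both paternal groups within a country, that odds ratios are estimated by country, and that incidence proportions are pooled as within-country risk ratios. That also stands and limits the consequence.

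A reader might go further than the documents allow in three ways:

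- **Sweden.** Its whole-pregnancy window might seem to contaminate the pooled CM result. Sections 9.5 and 9.7.6 keep Sweden out of that pool.
- **A Norway–Denmark gap in teratogen exclusions.** This would require the 12- and 22-week limits to apply to teratogens, which no section states.
- **Very early losses.** A loss at week 16, for instance, can enter only in Norway.

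**Conclusion.** The inconsistency is real: for CM in Norway and Denmark the maternal window ends at the index date and the maternal exclusions do not. Read literally, the exclusions use information from after the start of follow-up and remove long pregnancies more readily than losses. The case is clearest for teratogens and weaker for AEDs, where the figure references may imply a stop.

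What is at stake is the CM incidence proportions, the live/non-live mix and sensitivity analysis 4. A reader might infer a biased valproate odds ratio. The documents do not show one; that would need maternal dispensing after the index date to differ by the father's drug. The primary outcome analysis is not affected.

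The size cannot be derived from the protocol. The illustrated retention ratios for a week-22 loss, 1.005 to 1.18, rest on an assumed 1% to 30% chance of exclusion between conception and term, a constant hazard and a 40-week term.

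**What to change.** In sections 9.3.3, 9.3.3.2, 9.7.3 and 9.7.4, state that for CM in Norway and Denmark the maternal AED and teratogen exclusions use only exposure from three months before LMP2 up to the index date, in line with section 9.3.1.2. Report later maternal use descriptively.

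Optionally, add a sensitivity analysis for the two pooled countries with a common maternal window ending at week 12, to show how much the 10- versus 20-week difference matters. This should not replace the main rule: it would readmit Danish offspring with maternal exposure between weeks 12 and 22, including exposures that section 9.3.3.2 excludes for foetal toxicity.

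The cost is a wording change and, if the programs used the literal rule, one changed filter on data already extracted. Because the milestones show that results have been reported, that would mean re-running the CM analyses. The downside is that offspring whose first maternal exposure falls after the index date stay in the analysis.

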### 9.3.1.3 Classification of exposure

Particular care will be taken in the definition and classification of paternal exposure. Person-time exposed will be classified to take into account intensity of drug exposure during the 3-months pre-conception risk window using the longitudinal K-means clustering (R package kml) algorithm (15). This method allows for a more precise description of exposure of fathers to drugs and allows profiles to be distinguished improving evaluation of effects of drugs on outcomes. In summary the following steps apply:

- To quantify drug exposure, for each individual, prescription data will be transformed into the standard units of measurement of the World Health Organization (WHO): the Defined Daily Dose (DDD) (Figure 8). The duration of treatment and dates of exposure

 See footnote 10

will be estimated assuming individuals are exposed to one DDD per day and using information on number of units and dates of prescriptions, where available. For the father, drug prescribed and dispensed three months before the LMP2 date (including the LMP2 date) will be taken into account. A validation of the assumption that individuals are exposed to one DDD per day will be provided as a sensitivity analysis (section 9.7.5).

- After super imposing length of exposure onto the spermatogenic risk window, exposure data will be individually transformed into number of DDDs (Figure 8) dispensed during every 14 day interval within the 3-months exposure period. This way, the cumulative drug exposure of each father will be evaluated at several time points, and the exposure data will become longitudinal which will allow drawing individual trajectories of exposure through the pre-conception period. Data will be censored at the LMP2 date.
- In this study, clusters of fathers with homogenous trajectories of drug intake during the assessment period will be identified, using the number of DDDs in every 14 days interval and grouping fathers with similar “trajectories” of this metric over time. Since it will be assumed that treated fathers will be exposed to 1 WHO DDD per day, the number of DDDs in each 14-days interval also coincides with the number of days covered in the same period (e.g. 10 DDDs = 10 days covered in a specific 14-days interval). The longitudinal K-means clustering algorithm will be applied to create K clusters with homogenous trajectories, as empirically driven by the data. No assumption about the number of clusters is made prior to running the algorithm. Mean DDD trajectories will be plotted for each cluster and shape described. It is anticipated that several clusters of exposed fathers will be identified with homogenous trajectories of exposure during the 3-months risk window. For example, Cluster A = low constant exposure, Cluster B = decreasing exposure, Cluster C = moderate constant exposure, Cluster D = increasing exposure and Cluster E = high constant exposure.

The K-means is a novel method applied in studies investigating medication safety during pregnancy as it can model complex real-world exposures. This method proposed by Hurault-Delarue et al.(15) allows drug exposure during pregnancy to be modelled in a flexible way accounting for treatment intensity and evolution overtime. This methodology attempts to overcome some of the limitations associated with defining exposure using, for example binary classification (ever, never use) or the ‘Intention To Treat’ approach where dose is defined at one time point (e.g conception, or start of 3 months pre-conception period) since AED treatment may be modified if planning for,(or during) pregnancy.

In particular, K-means has been used to identify trajectories of higher or lower medication exposure in studies investigating the effects of maternal exposure to medication during or after pregnancy on infant outcomes, with data from secondary databases (such as electronic health records, prescription orders or dispensation information) (16). The application of this methodology for assessing paternal exposure in the population of this study is novel, albeit follows the same principles.

- Descriptive statistics will summarise distribution of exposure to each AED within each cluster.
- The empirically defined clusters will be used in the analyses of the study objectives. In the comparative analyses the exposure will be expressed as a dichotomous variable: exposure to valproate in monotherapy vs exposure to lamotrigine/levetiracetam in

---

monotherapy. The classification in cluster identified with the longitudinal K-means algorithm will be used to stratify the comparative analysis in cluster homogeneous for duration and intensity of exposure.

The K-means algorithm will be applied to maternal exposure within the 3-months period prior to LMP2 and during the reported period of gestation. However, since mothers exposed to AEDs will be excluded from the comparative analyses, these data will only be provided for descriptive purposes.

Active ingredient: valproic acid - ATC: N03AG01 - WHO DDD: 1.5 g

[figure not shown]

Figure 8: Calculation of paternal exposure in each 14-day interval during the 3-months risk window prior to conception

